#### 2.3.6.2 Clinical Laboratory Assessments

Safety endpoints related to clinical laboratory assessments include change from baseline and shifts from baseline in all safety laboratory parameters.

The following tests will be performed at the visits identified in the Time and Events Table (Table 1).

- Hematology: hemoglobin, hematocrit, RBC count, WBC count with differential, platelet count, mean cell hemoglobin, mean cell hemoglobin concentration, mean corpuscular volume, reticulocyte count and schistocytes;
- Serum Chemistry: liver panel (total, direct and indirect bilirubin, lactate dehydrogenase [LDH], AST, ALT), renal panel (BUN, creatinine), creatine phosphokinase (CPK), albumin, sodium, potassium, magnesium, bicarbonate, chloride, calcium, inorganic phosphorus, glucose, total protein, alkaline phosphatase, uric acid, serum amylase, serum lipase, and cystatin C; at specified visits, coagulation panel (PT, PTT, INR), lipid panel (HDL, LDL, Triglycerides, Total Cholesterol) will be included
- Urinalysis: At the central laboratory, nitrite, blood, and protein, will be tested. If positive, microscopy will be performed;
- Virology (measured only at screening): hepatitis B surface antigen, hepatitis C antibodies, HIV 1 and 2 antibodies; virology tests done within 6 weeks prior to screening are acceptable for eligibility assessment;
- TB screen: Only interferon  $\gamma$  release assay (IGRA) done within 6 weeks prior to screening is allowed for eligibility assessment.

#### 2.3.6.3 Vital Signs

Safety endpoints include change from baseline in vital signs. Vital signs will be measured during screening and on each as specified in Table 1. Vital signs assessments will be performed after the subject has rested for at least three minutes while seated, and will include the following:

- Blood pressure
- Pulse rate
- Body temperature

#### *2.3.6.4 Electrocardiogram*

Safety endpoints include clinically significant abnormal electrocardiogram (ECG) findings. A 12-lead ECG, after resting for at least 3 minutes, will be performed at screening and assessed for any clinically significant abnormalities. All abnormalities will be recorded in the EDC system. Assuming the ECG abnormality does not preclude study entry, an ECG may be repeated as clinically indicated.

#### *2.3.6.5 Physical Examination*

Safety endpoints include physical examination findings. A complete physical examination (including evaluation of general appearance/mental status, HEENT [head, eyes, ears, nose, throat], and the following body systems: dermatologic, cardiovascular, respiratory, gastrointestinal, musculoskeletal and neurologic) for safety, assessments will be performed at visits indicated in Table 1.

Body weight will be measured as part of the physical examinations. Height needs to be recorded at screening only. BMI will be calculated from the body weight and height measurements.

#### *2.3.6.6 ACTG-BPNST*

Safety endpoints include change from baseline in score on the AIDS Clinical Trial Group Brief Peripheral Neuropathy Screening Test (ACTG-BPNST). ACTG-BPNST will be completed by the study subject and the study doctor to assess changes in neuropathy. Proven translations will be used for non-English speaking subjects, whenever possible.

## **3 STATISTICAL METHODOLOGY**

### **3.1 General Considerations**

#### *3.1.1 Analysis Day*

Analysis day will be calculated from the date of first dose of study drug. The day of the first dose of study drug will be Day 1, and the day immediately before Day 1 will be Day -1. There will be no Day 0.

#### *3.1.2 Analysis Visits for Efficacy*

Scheduled visits will be assigned to analysis visits as recorded in the electronic data capture (EDC) system. If a scheduled visit is not available, unscheduled and early termination visits will be assigned to analysis visits using analysis visit windows based on the actual date the assessment took place. The start day of the analysis window will be calculated as the midpoint between the scheduled assessment and previously scheduled assessment for that parameter. The end day of the analysis window will be calculated as the midpoint between the scheduled assessment and the next scheduled assessment for that parameter. Where multiple measurements

for a particular parameter appear within an analysis window, the scheduled visit will be used. If no scheduled visit appears in the analysis window, the result closest to the target day will be used. If equidistant and both are unscheduled and/or early termination visits, the later result will be used for the summary measure.

Though all measures may not be used in data summaries (e.g., two lab measures within the same analysis visit window), all measurements appear in the datasets and listings. For subjects where the event date is missing, the study day and analysis window will also be missing. See the following table for an example of analysis windows.

Analysis Visit	Analysis Day Target	Analysis Day Window
Week 1	8	2 - 11
Week 2	15	12 - 22
Week 4	29	23 - 43
Week 8	57	44 - 71
Week 12	85	72 - 88
Week 13	92	89 - 102
Week 16	113	103 - 127
Week 20	141	128 - 155
Week 24	170	156 - 181
Week 28	198	$\geq 182$

### 3.1.3 *Definition of Baseline*

Baseline is defined as the last non-missing value prior to start of dosing with study medication (typically the Day 1 pre-dose value).

### 3.1.4 *Summary Statistics*

Categorical data will be summarized with counts and percentages of subjects. Continuous data will generally be summarized with descriptive statistics including n (number of non-missing values), mean, median, standard deviation, minimum, and maximum.

### 3.1.5 *Hypothesis Testing*

As this is an exploratory study in a rare disease, unless specified otherwise, all statistical tests and confidence intervals will be based on a 2-sided alpha of 0.10. No multiplicity adjustment will be applied to the multiple dose and multiple endpoints comparisons.

### 3.1.6 *Evaluation of Site Effect*

This is a multi-center study enrolling subjects from approximately 40 study sites across North America, Europe, and Australia and New Zealand. Site effect will not be evaluated since the number of subjects at each site is expected to be too small.

## 3.2 **Analysis Populations**

### 3.2.1 *Intent-to-Treat (ITT) Population*

The ITT Population is defined as all randomized subjects.

### *3.2.2 Intent-to-Treat (ITT) Population*

The ITT Population is defined as all randomized subjects who received at least one dose of study drug and have a baseline assessment and at least one post baseline efficacy assessment. This will be the primary analysis population for the evaluation of efficacy.

### *3.2.3 Per-Protocol (PP) Population*

The PP Population is defined as all subjects in the ITT Population who have  $\geq 80\%$  compliance with the study drug administration and do not have protocol deviations that could significantly affect the interpretation of the results for the primary endpoints. The PP Population will be a secondary population for analysis of the primary efficacy endpoint.

The following aspects will be considered for subjects to be excluded from the PP analysis:

- Subjects with significant protocol deviations regarding inclusion and exclusion criteria that may impact evaluation of the primary endpoints.
- Subjects with significant lack of compliance of study medication administration (CCX140-B /placebo) defined as: All subjects who were  $<80\%$  compliant with taking CCX140-B /placebo based on study medication accountability records.
- Subjects administered non-protocol allowed medications such as, calcineurin inhibitors, ACE-inhibitors or ARBs, spironolactone, eplerenone, antihypertensive, diuretics, immunosuppressants or calcineurin inhibitors or subjects with dose increases of such drugs during the course of the study.

Subjects to be excluded from the PP population will be identified and documented prior to the database lock and unblinding for analysis. A subject's data could be partially excluded from analysis depending on when the deviation occurred. For example, if a deviation occurred during the open-label extension (OLE) that did not impact the data from the double-blind period, only the data during the OLE will be excluded.

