6.8. Concomitant Medications and Restrictions

Medications taken prior to enrollment will be recorded:

- **rituximab or other B-cell depleting monoclonal antibodies for 1 year prior to screening;**
Subjects who have taken rituximab or other B-cell depleting monoclonal antibodies but stopped more than 20 weeks before screening will be allowed to participate if the recovery of the B cell population to within normal range is confirmed at the time of screening.
- **all FSGS medications (specifically glucocorticoids, immunosuppressives) for 6 months prior to screening;**

- **all other medications, including plasma therapy regimens, for 12 weeks prior to screening.**

In order not to disrupt subject care, the protocol will allow continuation of treatment (background medications) with glucocorticoids, immunosuppressants, calcineurin inhibitors, or renin-angiotensin-aldosterone system (RAAS) blockers. The doses for these background medications must remain stable for a minimum of 4 weeks prior to screening and through the treatment period (24 weeks) following randomization, with the following exceptions. Adjustment of RAAS blockers is permitted for management of hypertension. During the open label period (after Week 12), glucocorticoids, immunosuppressants, and calcineurin inhibitor will be allowed only if essential for patient safety.

Experimental drugs, rituximab, and plasmapheresis are not allowed at any point during the course of the study. If the Investigator deems that any of these treatments are necessary for the best interest of a subject, this subject would discontinue study drug, but remain in the study to monitor outcomes.

CCX140-B is primarily cleared through CYP3A4 metabolism. Subjects taking strong CYP3A4 inducers (e.g., phenytoin, rifampicin, carbamazepine, St. John's Wort) or strong CYP3A4 inhibitors (e.g., boceprevir, clarithromycin, conivaptan, grapefruit juice, indinavir, itraconazole, ketoconazole, lopinavir/ritonavir, mibefradil, nefazodone, nelfinavir, posaconazole, ritonavir, saquinavir, telaprevir, telithromycin, and voriconazole) will be excluded from this clinical trial since these drugs may substantially increase the CCX140-B plasma levels.

Subjects taking lithium, **pamidronate**, interferon, **or chronic NSAIDS** are also excluded. Note that subjects taking intermittent NSAIDS for pain or fever are discouraged from study participation, but **are** not excluded.

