## Responder Analyses

The response rate across dose groups for patients achieving 30% reduction in UPCR (whenever available 24-hour urine evaluations will be used) from baseline at Week 12 will be calculated, with the number of subjects in the respective treatment group in the ITT (or PP) population being the denominator. The 90% Clopper-Pearson exact CIs will be estimated for the response rates in each treatment group. The estimated difference and its associated 90% CIs of response rates between each of the CCX140-B (5, 10, or 15 mg) groups and the placebo group will be provided using stratified analysis using the Newcombe hybrid-score method. The Stratification factors are the same as used in the randomization: UPCR  $<3.5$  g protein/g creatinine versus UPCR  $\geq 3.5$  g protein/g creatinine at baseline and by the current use of glucocorticoids and/or immunosuppressive medications (yes vs no) if there are enough responders. If there are not enough patients in any strata, the stratification variable will be removed from the model.

Non-responder imputation for non-allowed medications:

All subjects who started new therapy or increased the doses of an existing therapy that is clinically significant and was not allowed per protocol will be imputed as non-responders for the responder analysis. For example, the new use or clinically significant increase doses of an angiotensin converting enzyme (ACE) inhibitor, angiotensin receptor blocker (ARB) or other blocker of the renin angiotensin aldosterone system (RAAS) or new use of glucocorticoids, a calcineurin inhibitor or other immunomodulatory or immunosuppressive therapy will be reviewed before database lock.

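### The SAP's per-protocol exclusion list names drug classes the protocol allows and omits its dose-change exceptions, so protocol-compliant subjects can be put forward for exclusion

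*SAP*

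**What the plan says.** The third bullet of SAP 3.2.3 describes a ground for leaving the per-protocol (PP) set: "Subjects administered non-protocol allowed medications such as, calcineurin inhibitors, ACE-inhibitors or ARBs, spironolactone, eplerenone, antihypertensive, diuretics". It continues: "immunosuppressants or calcineurin inhibitors or subjects with dose increases of such drugs during the course of the study". No exception is attached to either part.

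The protocol treats these drugs differently:

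- Section 6.8 lets subjects continue glucocorticoids, immunosuppressants, calcineurin inhibitors and RAAS blockers at stable doses. It adds: "Adjustment of RAAS blockers is permitted for management of hypertension". Inclusion criterion 7 in Section 5.2 makes the same exception for the period to Week 12.
- The Synopsis (Methodology) and Section 4 say doses of RAAS blockers, glucocorticoids and immunosuppressive drugs are to be held constant, except where a change is needed for patient safety (Synopsis) or well-being (Section 4).
- For other medications, which would include diuretics and other antihypertensives, Section 4 asks the investigator to try to keep doses fixed in the blinded period. No section prohibits them.
- Section 6.8 bars three things throughout the study: experimental drugs, rituximab and plasmapheresis. The SAP bullet names none of them.

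Two other SAP analyses use a related idea. The non-responder rule (SAP 3.4.1, Responder Analyses) covers new or increased therapy that is both clinically significant and outside what the protocol allows. Its first example is "the new use or clinically significant increase doses of an angiotensin converting enzyme (ACE) inhibitor, angiotensin receptor blocker (ARB", extended to other RAAS blockers. Sensitivity analysis 3 carries the last observation forward once a non-allowed medication has been initiated, without defining that term.

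**The concern.** The bullet puts a protocol-breach label on classes that the protocol accepts, and "or subjects with dose increases of such drugs during the course of the study" takes in changes that the protocol expressly permits. Under SAP Section 1 and Protocol Section 9 the SAP supersedes the protocol on analysis, so the conflict cannot be assumed to resolve in the protocol's favour. SAP Section 6 does not declare it as a change.

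Three analyses turn on what counts as non-allowed: PP membership, non-responder status and the carry-forward in sensitivity analysis 3. Each words the trigger differently, so one subject could be handled in three ways. With about 10 subjects per arm, a few such decisions are visible in the results.

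**Working it through.** **Step 1. Compare the texts case by case.**

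| Case | Protocol | SAP 3.2.3 (PP) | Non-responder rule | Sensitivity 3 |
|---|---|---|---|---|
| Stable background immunosuppressant, calcineurin inhibitor or RAAS blocker | Allowed (6.8) | Class named | Not caught: needs a new start or increase | Not caught: nothing initiated |
| Stable diuretic or other antihypertensive | Not prohibited | Class named | Not caught; not among the examples | Not caught |
| RAAS increase for hypertension | Permitted (5.2, 6.8) | Caught by the dose-increase clause | Outside the rule's condition, but matches its example if clinically significant | Increases not mentioned |
| Immunosuppressant or calcineurin inhibitor increase for safety or well-being | Excepted (Synopsis, Section 4) | Caught by the dose-increase clause | Turns on which protocol passage is applied | Increases not mentioned |
| New or unjustified increase of these drugs in the blinded period | Breaks the stable-dose requirement | Caught | Caught if clinically significant | New start caught; increase not mentioned |

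The PP list is right in the last row. In the first two rows it names classes whose use complies with the protocol. In rows three and four it omits exceptions that the protocol states. For row four, Section 6.8 does not repeat the safety or well-being exception for the blinded period, so a flag has to say which protocol passages it follows.

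**Step 2. Reproduce the plan's precision figure.** Inputs are from Protocol 9.4 and SAP 2.2.4: SD 0.70 for change in log UPCR, 10 per group, 90% interval.

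Half-width = t(0.95, 2n−2) × 0.70 × √(2/n). With n = 10: 1.734 × 0.70 × √0.2 = 0.543, as stated. At a ratio of 0.5 the interval is 0.5 × exp(±0.543) = (0.29, 0.86), also as stated.

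**Step 3. Vary the loss from the PP set.** The number of subjects affected is not in the documents, so the loss is an assumption. The table takes equal loss in both arms, an unchanged SD and the same simple t interval.

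| Lost per arm | n per arm | Half-width | Change | 90% CI at ratio 0.5 |
|---|---|---|---|---|
| 0 | 10 | 0.543 | – | 0.29 to 0.86 |
| 1 | 9 | 0.576 | +6% | 0.28 to 0.89 |
| 2 | 8 | 0.616 | +14% | 0.27 to 0.93 |
| 3 | 7 | 0.667 | +23% | 0.26 to 0.97 |
| 4 | 6 | 0.732 | +35% | 0.24 to 1.04 |

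Example for two lost: 1.761 × 0.70 × √(2/8) = 0.616.

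**Step 4. Responder analysis.** The denominator is the arm, so one responder reclassified moves the rate by 1/10 = 10 points. For a permitted RAAS increase this arises only if the example is applied over the rule's own condition.

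**The case against.** A reader might infer that compliant subjects are automatically dropped from the PP set, that most subjects on standard background care would go, and that the same subjects are counted as non-responders. The documents do not support this:

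- **Exclusion is not automatic.** The bullets are introduced by "The following aspects will be considered for subjects to be excluded from the PP analysis". The decision is blinded: "Subjects to be excluded from the PP population will be identified and documented prior to the database lock and unblinding for analysis". It can also be limited in time: "A subject's data could be partially excluded from analysis depending on when the deviation occurred".
- **The opening phrase can be read as a limit.** On that reading the classes only illustrate use that breaks the protocol. The SAP's Covariates and Subgroups section plans analyses by calcineurin inhibitor, RAAS blocker, diuretic and antihypertensive use, so it expects users of these drugs in the efficacy analyses.
- **The non-responder rule is separate.** It does not cite the PP list, and on its operative words a RAAS adjustment that the protocol permits is not imputed. Its examples are for review before lock.
- **Sensitivity analysis 3 acts on initiation.** Stable background therapy does not trigger it.
- **A permitted change can still confound.** Section 4 wants constant doses because changes could influence the assessments, and that holds whatever the reason for the change.

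All of this stands, and it sets the limits of the point. It does not rescue the dose-increase clause, which is a separate limb and carries no exception. Nor does it supply one definition for the three analyses. Blinded review guards against bias, but the reviewers need a rule, and the written one conflicts with the protocol.

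**Conclusion.** The point holds in limited form. SAP 3.2.3 is wrong as written: it labels as non-allowed several classes that the protocol allows as stable background or never prohibits, and its dose-increase clause drops the stated exceptions. Compliant subjects can be put forward for PP exclusion. It does not follow that they will be excluded. For the non-responder rule the defect is an unqualified RAAS example; for sensitivity analysis 3 it is an undefined term that covers initiation only.

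The primary MMRM in the ITT population does not use any of these rules, and PP is a secondary population in a study described as exploratory. The widening to 0.576 or 0.616 rests on an assumed loss of 1 or 2 per arm and the simplifications in step 3. It shows scale and is not a forecast. This should be corrected, but it does not threaten the main analysis. No view is taken on which clinical rule is right; the passages must be reconciled.

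**What to change.** Reconcile SAP 3.2.3, the non-responder rule and sensitivity analysis 3 with the protocol Synopsis (Methodology) and Sections 4, 5.2 and 6.8:

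1. Take stable background therapy and classes the protocol does not prohibit off the PP exclusion list.
2. Define one subject-level flag, a new start or dose increase that the protocol does not permit, and cite the protocol passages that set the exceptions. Use it in all three analyses, each with its own further conditions stated.
3. Add the hypertension exception to the RAAS example in the non-responder rule, and say whether sensitivity analysis 3 covers dose increases.
4. If the sponsor wants to set aside permitted RAAS changes because they may affect UPCR, make that a separate, labelled confounding-medication sensitivity analysis, not a protocol deviation.

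The cost is SAP wording. The flag can be set in the blinded pre-lock review already planned, using concomitant medication data that Protocol 6.8 requires. The review will need the reason for each dose change; the documents do not say whether the case report form records it.

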### *3.2.4 Safety Population*

The Safety Population is defined as all randomized subjects who received at least one dose of study drug. All safety data will be analyzed using the Safety Populations by the treatment groups that subjects are randomized to. In the event that a subject takes the wrong study drug (i.e., did not take the randomized study drug), the actual treatment received will be used for analysis.

#### Notations for Treatment Groups

Period A: initial 12-week blinded treatment period, Day 1 –Week12

Period B: open-label treatment period plus 4 Weeks of Follow-up, Week 12 to End of Study (EOS)

We have defined 3 Safety Populations for this study:

1. The Safety Population in Period A (Safety\_A) is defined as all subjects who received at least one dose of study drug in Period A.
2. The Safety Population in Period B (Safety\_B) is defined as all subjects who received at least one dose of study drug in Period B.
3. The All CCX140-B Treated Population is defined as all subjects received at least one dose of CCX140-B in the study.

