9.3.6. Safety Analyses

All clinical safety and tolerability data will be listed by treatment group and by subject, and will be summarized by treatment group and visit.

Treatment-emergent adverse events (TEAE) will be summarized for each treatment group by MedDRA System Organ Class (SOC) and preferred term (PT), by relatedness and maximum severity. Treatment-emergent serious adverse events (TESAE) and TEAE leading to study withdrawal will be separately listed and may be summarized if warranted by the subject incidences.

Vital signs and laboratory test results, and their changes from baseline will be summarized by treatment group and visit. Abnormal laboratory values will be flagged in the data listing. Shift tables will be generated by study visit.

Individual ECG findings and change from baseline in ECG findings will be listed by treatment group, subject, and study visit, and summarized by treatment group and visit.

Findings from physical examinations will be listed.

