### 2.3.6 Safety Endpoints

#### 2.3.6.1 Adverse Events

Safety endpoints related to adverse events include subject incidence of treatment-emergent adverse events (TEAE), adverse events leading to study withdrawal, and serious adverse events. An adverse event will be considered treatment-emergent if the start date of the event is on or after the date of administration of the first dose of study medication.

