## 3.6 Safety Assessment

Safety analyses will be performed for the Safety Population. All safety assessments will be based on actual treatments received by participants.

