### 3.6.1 Adverse Events (AEs)

An overview of AEs will be provided including counts and percentages of subjects (and event counts) with the following:

- Any TEAEs (overall and by maximum severity)
- Any study drug related TEAEs (overall and by maximum severity)
- Any treatment-emergent serious AEs (TESEAEs)
- Any TEAEs leading to discontinuation of study drug
- Any AEs leading to death

Counts and percentages of subjects (and event counts) will also be presented by system organ class (SOC) and preferred term (PT) using the Medical Dictionary for Regulatory Activities (MedDRA) Version 20.1 any TEAEs and TESEAEs for 3 Safety Populations separately. Counts and percentages of subjects (and event counts) will also be presented by PT in decreasing frequency for any TEAEs and TESEAEs for 3 Safety Populations (see 3.2.4 for definitions) separately.

TEAEs for the Safety Population in each period are defined as an event with a start date on or after the first study drug treatment in each period and up to the final observation in each period. Treatment periods for analysis of adverse event are defined in Section 3.2.4. TEAEs for the All CCX140-B Treated Population are defined as an event with a start date on or after the first dose of CCX140-B up to the final observation.

Listings will be presented specifically for SAEs and TEAEs leading to discontinuation of study drug.

The severity of AEs was assessed by the investigator using the following protocol definitions:

- Mild (Grade 1): no limitation of usual activities
- Moderate (Grade 2): some limitation of usual activities
- Severe (Grade 3): inability to carry out usual activities
- Life-threatening (Grade 4): an immediate risk of death
- Death (Grade 5)

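### TEAEs that start after Week 12 in subjects with no open-label dose are in neither period's SOC/PT table and, for placebo subjects, in none of the three

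*SAP*

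**What the plan says.** SAP 3.2.4 divides the study in two. The first part is "Period A: initial 12-week blinded treatment period", from Day 1 to Week 12, with no follow-up attached. The second is "Period B: open-label treatment period plus 4 Weeks of Follow-up, Week 12 to End of Study (EOS". Safety_A holds subjects dosed in Period A. Safety_B "is defined as all subjects who received at least one dose of study drug in Period B". The third population, All CCX140-B Treated, holds everyone who ever took CCX140-B.

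For the two period populations, SAP 3.6.1 takes a TEAE to be one "with a start date on or after the first study drug treatment in each period and up to the final observation in each period". For All CCX140-B Treated, the window runs from the first CCX140-B dose to the final observation and is not cut at Week 12. The SOC/PT counts are made for these three populations, and the PT counts are likewise "presented by PT in decreasing frequency for any TEAEs and TESEAEs for 3 Safety Populations".

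Three wider provisions also bear on the point. SAP 2.3.6.1 calls an event treatment-emergent if the "start date of the event is on or after the date of administration of the first dose of study medication", with no end date. SAP 3.6 opens with "Safety analyses will be performed for the Safety Population". Protocol 9.3.6 states: "Treatment-emergent adverse events (TEAE) will be summarized for each treatment group by MedDRA System Organ Class (SOC) and preferred term (PT", followed by relatedness and maximum severity.

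SAP 2.2.1 is written as if every subject goes on to open-label drug. However, SAP Table 1 (footnotes 6 and 7) and protocol 5.4, 7.12 and 8.5 provide for subjects who do not. Their last visit is Week 16, and AEs are recorded there. Protocol 4 and 5.5 keep earlier stoppers in the study, and protocol 8.2.3 continues AE reporting after study drug stops.

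**The concern.** Follow-up belongs to Period B alone, yet entry to the Period B population needs a dose in that period. A subject who takes no open-label drug still has follow-up time and AE collection after Week 12, but no period table in which a new event can be counted. For a placebo subject the third population is closed as well.

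Safety and tolerability is the primary safety objective. Under protocol 5.4, the reasons for not continuing include a new infection or a need for new immunosuppression, and protocol 4 places infection among the adverse events of special interest. Off-treatment events in these subjects are therefore worth showing by type. Under the current rules the active-arm events appear by type in one table and the placebo events in none, and nothing tells the reader that events were left out.

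**Working it through.** The plan gives no figure to reproduce. The check applies the SAP's membership rules and TEAE windows to each type of subject, then measures the uncovered time.

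**Inputs.** Week 12 is Day 85, Week 16 is Day 113 and Week 28 is Day 198 (SAP Table 1). Protocol 7.12 puts the Week 16 follow-up at Day 114. The visit window is ±3 days at Week 12 (protocol 7.7) and at Week 16 (protocol 7.12).

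**Rules.**
- Safety_A table: onset from Day 1 to Week 12.
- Safety_B table: the subject has a Period B dose, and onset falls from that dose to the final observation.
- All CCX140-B Treated table: onset from the first CCX140-B dose to the final observation.

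| Arm | Open-label dose | Onset day | Safety_A | Safety_B | All CCX140-B Treated |
|---|---|---|---|---|---|
| Placebo | No | 40 | Yes | No | No |
| Placebo | No | 90 or 110 | No | No | **No** |
| Placebo | Yes | 40 | Yes | No | No |
| Placebo | Yes | 90 or 110 | No | Yes | Yes |
| Active | No | 40 | Yes | No | Yes |
| Active | No | 90 or 110 | No | No | Yes |
| Active | Yes | 40 | Yes | No | Yes |
| Active | Yes | 90 or 110 | No | Yes | Yes |

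Only subjects without an open-label dose fall outside both period tables, and only placebo subjects fall outside all three. Every event in the grid meets the open-ended definition in SAP 2.3.6.1.

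**Uncovered days per subject followed to Week 16** = day of the Week 16 visit − last day of Period A.
- Nominal days: 113 − 85 = 28, or 114 − 85 = 29 with the protocol 7.12 day.
- Period A fixed at Day 85, Week 16 window applied to both target days: earliest (113 − 3) − 85 = 25, latest (114 + 3) − 85 = 32.
- Period A ending at the actual Week 12 visit (Day 82 to Day 88): shortest 110 − 88 = 22, longest 117 − 82 = 35.

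**Early stoppers.** For a last dose on Day 57, 57 + 28 = Day 85. Anyone who stopped on or before Day 57 and stays in the study is therefore more than 28 days off drug for every event from Day 86 onward.

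**The case against.** The strongest reply is that very little is lost, and this stands. SAP 7 puts all available data in listings. The AE overview in SAP 3.6.1 is not tied to the three populations, so under SAP 2.3.6.1 and 3.6 it can count these events as any, related, serious, leading to discontinuation or fatal. It does not show them by SOC or PT.

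A second reply is that the SAP supersedes the protocol, so it may narrow protocol 9.3.6. It may, but SAP 6 lists only the responder analysis and MCP-MOD as changes, so nothing shows that the narrowing was intended.

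A third is that leaving out events long after an early stop is defensible. Protocol 7.14 sets the final safety visit 4 weeks after stopping drug, and protocol 8.2.5 continues SAE reporting for 28 days. This stands in part: such events should be distinguishable from those in the 4-week follow-up, and a table that mixed the two would mislead.

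A reader might also infer two stronger points that the documents do not support.
- That the missing table would supply a placebo comparison for follow-up. It would not. Subjects without an open-label dose are selected after randomisation by infection, need for new treatment, withdrawal or the stopping guidelines, any of which treatment may affect. The randomised safety contrast ends at Week 12, and Safety_A covers it.
- That the boundary between periods is unusable, because both periods name Week 12 and protocol 7.7 allows a dose at that visit. Period B is labelled open-label, the Time and Events Table starts open-label dosing in the Day 85 column, and SAP 3.3.7 splits exposure at Days 85 and 86 (for exposure, not AEs). The natural reading is clear. Counting a blinded Week 12 dose as a Period B dose would in fact close the gap for those subjects, by placing people who never took open-label drug in the open-label population. One clarifying sentence is enough.

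**Conclusion.** The point holds as a minor one. On the SAP's own rules, TEAEs starting after Week 12 in subjects with no open-label dose are missing from both period SOC/PT and PT-frequency tables, and placebo subjects' events are missing from all three. The by-arm SOC/PT summary called for in protocol 9.3.6 is incomplete to that extent.

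The uncovered time is about 28 days per subject followed to Week 16, assuming that Period A ends on Day 85. It is 25 to 32 days with the Week 16 window and its two target days, and 22 to 35 days if Period A ends at the actual Week 12 visit. Subjects who leave the study earlier contribute less or nothing. The documents do not give the number of subjects affected; the planned placebo arm of 10 caps those absent from all three tables.

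A reader might infer that CCX140-B safety events disappear or that the blinded comparison is biased. Neither follows. Every CCX140-B subject's events remain in the All CCX140-B Treated table, and the Day 1 to Week 12 comparison is unaffected.

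**What to change.** Add a rule to SAP 3.6.1: for subjects with no open-label dose, TEAEs with onset after Period A and up to the last follow-up observation are tabulated by SOC and PT under the randomised arm, placebo included, in a separate off-treatment follow-up table. Label the table descriptive, because its subjects are selected after randomisation. Show time since last dose, so that early stoppers' late events can be told apart from those in the 4-week follow-up.

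Keep Safety_A as the common Day 1 to Week 12 window. State in SAP 3.2.4 that a Period B dose means an open-label dose, and in SAP 3.6.1 that the AE overview uses the open-ended definition in 2.3.6.1.

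The cost is a few SAP sentences, a flag and a time-since-last-dose variable in the AE dataset, and one small table. No new data are needed. The downside is that the table will be sparse and is not a randomised comparison.
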